1. WHT treatment group: patients admitted to the MPP during a predefined 12-month period who consented to participate in the study.
2. MPM control group: patients from MPM clinics within Geisinger during the same 12-month period.
3. Historic MPP control group: patients who completed the MPP 12 months before the start of this study (ie, before WHT was introduced to the MPP in August 2017).

**Study Design:** This is a prospective, non-randomized, non-blinded trial with historic and concurrent controls to assess the effect of the addition of WHT (Apple Watch, iPhone, Pain App, and physician and patient dashboards) on patient and health system outcomes. The WHT intervention group will include patients enrolled in the Geisinger's MPP Program over 1 year, with 1 year of follow up. Patients in the WHT group will be compared to patients in 2 control groups: patients enrolled in the MPP in the preceding year (historic control group), and patients enrolled on the MPM over the same period (concurrent control group).

The WHT intervention will consist of the following:

- Patient and HCP tracking of patient-reported pain, pain management, disability, depression and medication usage over time
- Patient and HCP tracking of quality of sleep and activity over time
- Prompts to patients to engage in self-care, including non-pharmaceutical pain management therapies consistent with their MPP training
- HCP alerts if patients exceed pre-specified thresholds in pain or functioning

Patients will use the WHT 20 hours per day, every day for a period of 12 months.

Patients will attend study visits at baseline and months 2, 4, 6, 8, 10 and 12. Patients consented into the WHT group will participate in the study for 12 months from the day of enrollment.

Outcome data for control patients will be collected retrospectively from the electronic health record (EHR). Assessments will have occurred as part of their standard of care.

Twelve months of enrollment, with 12 months of follow-up, for a total of 24 months.

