**Estimated Study Duration:**

Outcome Measures:	Study Aim 1 (Between- Group Differences)
	
 
• Primary Clinical Endpoints 
 
○ A difference in the change in pain scores over time from baseline to month 12 (M12) as measured by the Numerical Pain Score (NPS)
 
○ A difference in the change in depression scores over time from baseline to M12 as measured by the Patient Health Questionnaire (PHQ-9)
 
○ A difference in the change in pain medication use over time from baseline to M12, calculated as mean daily morphine equivalents (MEQs)
 
 
 
• Secondary Clinical Endpoints 
 
○ A difference in the change in physical function/disability over time from baseline to M12 as measured by the Oswestry Disability Index (ODI)
 
 
 
• Endpoints Related to Resource Utilization 
 
○ A difference in the change in healthcare resource utilization over time (quarterly) from baseline to M12: number of hospitalizations, emergency department (ED) visits, inpatient, outpatient visits, rehabilitation visits, and pharmacy/medication orders
 
○ A difference in the change in healthcare costs over time (quarterly) from baseline to M12: total, inpatient, outpatient, rehabilitation, and pharmacy
 
 
 

	Study Aim 2 Comparisons within WHT Group

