Sample Size:	
 
• Sleep: change in number of hours and number of restful hours per night over time from month 1 (M1) to M12
 
• Activity level: change in number of steps and minutes of exercise per day over time from M1 to M12
 
• Daily pain scores: change in worst pain of the day (mean value for the month), number of episodes of breakthrough pain (episodes per 7 days), and mean level of breakthrough pain (mean value for month) over time from M1 to M12
 
 
Sample size estimated to be at least 240 WHT patients, 1000 MPM patients, and 150 historic MPP patients. Based on these sample sizes, and assuming a 10% drop-out rate, detectable effect sizes at 80% power for the primary clinical outcomes as analyzed by repeated measures analysis of variance (ANOVA) model and using an omnibus F test (difference in changes between the groups at any time) are:
 
 
• NPS: 0.35 versus MPM; 0.42 versus historic MPP
 
• PHQ-8: 1.40 versus MPM; 1.81 versus historic MPP
 
• MEQs: 11.51 versus MPM; 17.58 versus historic MPP
 

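### Does the PHQ-8 label on the depression power figures leave the PHQ-9 primary endpoint without a usable power statement?

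*Combined protocol and SAP*

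**What the plan says.** In the Protocol Synopsis, Outcome Measures, Study Aim 1, the second of three primary clinical endpoints is "A difference in the change in depression scores over time from baseline to M12 as measured by the Patient Health Questionnaire (PHQ-9"). That is the only place where the PHQ-9 is named.

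The Sample Size section starts from the group sizes: "Sample size estimated to be at least 240 WHT patients, 1000 MPM patients, and 150 historic MPP patients". It then adds a loss allowance, "assuming a 10% drop-out rate", and reports "detectable effect sizes at 80% power for the primary clinical outcomes", based on an omnibus F test in a repeated measures ANOVA. The depression line reads "PHQ-8: 1.40 versus MPM; 1.81 versus historic MPP". That is the only place where the PHQ-8 is named. The other two lines, for NPS and MEQs, carry the same names as their endpoints.

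The section gives no SD, within-patient correlation, alpha or number of time points for any of the three outcomes.

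**The concern.** A power statement should refer to the variable that will be tested. Here the endpoint list and the power statement name different versions of the questionnaire for one of three primary outcomes, and no sentence says that one stands in for the other. Because the inputs are missing, a reader cannot work back to the version that produced 1.40 and 1.81.

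If the variability came from a shorter score, the SD of the analysed score could be larger than the calculation assumed. The detectable differences would then be understated, or the power to detect the stated differences would be below 80%. The study would have claimed slightly more sensitivity for depression than it has.

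**Working it through.** **Inputs from the Sample Size section.** Group sizes are 240 (WHT), 1000 (MPM) and 150 (historic MPP). With 10% drop-out applied to every group they become 216, 900 and 135. Power is 80%, and the stated differences are 1.40 and 1.81.

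**Assumptions, not in the document.** Two-sided alpha is 0.05. The two versions have eight and nine items on the same item scale. The covariance over time scales uniformly with the SD.

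**1. Can the stated figures be reproduced?** No, because no SD is given. Back-solving with the two-means approximation, SD = δ / [(1.960 + 0.842) × √(1/n₁ + 1/n₂)]:

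- MPM: √(1/216 + 1/900) = 0.0758, so SD = 1.40 / (2.802 × 0.0758) ≈ 6.6.
- Historic MPP: √(1/216 + 1/135) = 0.1097, so SD = 1.81 / (2.802 × 0.1097) ≈ 5.9.

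One common SD would make the ratio of the two differences 0.1097 / 0.0758 ≈ 1.45. The stated ratio is 1.81 / 1.40 = 1.29. The same ratio is 0.42 / 0.35 = 1.20 for NPS and 17.58 / 11.51 = 1.53 for MEQs. A single-SD calculation therefore does not give both figures for any of the three outcomes, including the two whose labels agree. This does not identify the questionnaire version, and it is not evidence that the depression line is in error.

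**2. If the label is a slip.** The figures are PHQ-9 figures and nothing moves.

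**3. If the figures belong to an eight-item score.** The detectable difference scales with the SD:

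| Behaviour of the extra item | SD factor | vs MPM | vs historic MPP |
|---|---|---|---|
| No variance | 1.000 | 1.40 | 1.81 |
| Uncorrelated, equal variance: √(9/8) | 1.061 | 1.485 | 1.920 |
| Perfectly correlated, equal variance: 9/8 | 1.125 | 1.575 | 2.036 |

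**4. Power if the true difference stays at 1.40 or 1.81.** Take F with T−1 and (N−2)(T−1) degrees of freedom, for T = 2 to 7 time points. The noncentrality needed for 80% power runs from 7.86 to 13.64 (MPM) and from 7.89 to 13.67 (historic MPP). For a fixed pattern of differences over time, noncentrality varies as 1/SD².

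- SD × 1.061: divide by 1.125. For MPM, 7.86 / 1.125 = 6.99 and 13.64 / 1.125 = 12.12. Power is 75.2% (T = 2) down to 74.3% (T = 7).
- SD × 1.125: divide by 1.125² = 1.2656. For MPM, 7.86 / 1.2656 = 6.21 and 13.64 / 1.2656 = 10.78. Power is 70.2% down to 68.2%.

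The power figures are the same for the historic comparison.

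**5. Is the low end coherent?** The factor 1.125 needs a ninth item that moves in lockstep with the other eight. Such an item would ordinarily raise the group difference by 9/8 as well. Noncentrality is then multiplied by 1.125² / 1.125² = 1, and power is exactly 80%. The 68% to 70% range needs the item to be perfectly correlated with the rest and yet add nothing to the group difference.

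**6. Does any decision depend on the label?** The order of the Sample Size section answers this. The group sizes come first and the differences are derived from them. Neither 1.40 nor 1.81 is called a target or a clinically important difference. Revising either would leave the 240, 1000 and 150, the endpoint, the group-by-time model and the F test as they are.

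**The case for a change.** The best case for acting is that only the sponsor can say whether this is a typing slip. Until it does, the power statement for a primary endpoint names something that is not the endpoint, and correcting it would cost almost nothing. A practical point adds to this. In the WHT arm, depression is part of "Patient and HCP tracking of patient-reported pain, pain management, disability, depression and medication usage over time", whereas control outcomes come retrospectively from health records, where "Assessments will have occurred as part of their standard of care". The sponsor cannot choose which version those records hold, so naming one version and confirming identical scoring would be prudent.

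The mismatch stands, and the document cannot settle its origin. The rest goes beyond it. The Study Design text does not mention the PHQ and gives no sign that the versions differ between arms. How the questionnaire is scored from two data sources is a separate matter of data handling, and relabelling the power line would not settle it. Listing the SD, correlation and number of time points would help a reader, but their absence affects NPS and MEQs equally and is unremarkable in a synopsis. None of this shows that 1.40 or 1.81 is wrong.

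**Conclusion.** No change to the plan follows. The two labels disagree, most plausibly through a slip of one digit, and the Outcome Measures section is the text that fixes what is analysed: the PHQ-9. An analyst working from it would not be misled by the label in the power line.

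The effect is nil if the label is a slip. If the figures are eight-item figures, the detectable differences rise by at most 0.18 points against MPM (1.575 − 1.40 = 0.175) and 0.23 points against historic MPP (2.036 − 1.81 = 0.226). That range rests on one added item of equal variance on the same scale, correlated between 0 and 1 with the others, or of no variance at all. It is not a strict bound: a more variable item could exceed it, and a negatively correlated one could lower the SD. The power figures also assume two-sided alpha of 0.05, 10% loss in every group and uniform scaling over time. Under any of these cases the group sizes, endpoint, test and interpretation of the result stay the same.

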## Protocol Synopsis

**Protocol  
Number:**

2017-0196

**Title:** Effect of Wearable Health Technology on Patients Treated for Chronic Pain at Geisinger Health System

**Sponsor:** Purdue Pharma L.P.  
[name]  
[name]  
[name]

**Study Phase:** Phase 4

**Study Sites:** The study will be conducted in the United States at 1 site, the Multidisciplinary Pain Program at Geisinger Health System

**Indication:** Chronic Pain

**Background:** Care for the chronic pain patients can be challenging. Providers are dependent on patients' recall of their symptoms between visits to gauge disease severity and treatment progress. Providers often lack timely access to patients' data on symptom severity, thereby limiting the providers' ability to effectively manage and optimize long-term treatment regimens for their patients.

Recent use of wearable health technology (WHT) has been effective in improving patient outcomes. Many wearable biosensors and their applications have been introduced in different stand-alone or interactive formats. WHT apps may have interactive capabilities involving active health or behavior change information that collects data from the user. WHT can detect abnormal and unforeseen situations and monitor physiological parameters and symptoms through these trackers. This technology has transformed healthcare by allowing continuous monitoring of patients without hospitalization. Medical monitoring of patients' body temperature, heart rate, brain activity, muscle motion and other critical data can be delivered through these trackers. When integrated with an expert-directed chronic pain intervention program like Geisinger's Multidisciplinary Pain Program (MPP), WHT (eg iPhone, Apple Watch) may improve comprehensive patient management and outcomes for patients living with chronic disease. WHT can also provide real-time data, allowing a healthcare provider to engage in more proactive patient care.

**Objectives** To assess whether the addition of WHT to the Geisinger MPP leads to improvements in clinically meaningful patient outcomes, reductions in healthcare utilization and costs.

**Patient Population:** The study population will be adult ( $\geq 18$  to  $< 76$  years) chronic pain patients being treated at pain clinics in the Geisinger healthcare system.

There will be 3 study groups, a WHT treatment group, a concurrent Medical Pain Management (MPM) control, and an historic MPP control:

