Statistical Methods:	
For clinical outcomes (primary, secondary, and exploratory), the effects of WHT will be quantified by calculating the change from baseline in clinical outcome variables in the WHT group over 12 months. For primary and secondary outcomes that are measured in the WHT group plus at least 1 control group, generalized linear modeling or nonparametric methods (depending on the score distributions) will be used to compare outcomes across the cohorts. Patient demographic and clinical characteristics that differ between groups at baseline will be included in multivariate adjusted models.
 
Repeated measures models will be used to generate point estimates and 95% confidence intervals (CIs) for least square mean (LSM) differences, odds ratios (ORs), or risk ratios (RRs). Where appropriate an overall F statistic will be generated to compare the change in groups across the study period (interaction of group*time).
 
For the analysis of healthcare utilization, a log-link function with a Poisson or negative binomial distribution will be used. For cost outcomes, a log-link function with a gamma distribution will be used. Otherwise, the same techniques described above (eg, GLM methods to account for matched groups, estimates, and CIs) will be used.
 
For analysis related to clinical outcomes collected only in the WHT group, the effects of WHT will be quantified by calculating the change from baseline over 12 months and using repeated measures ANCOVA models to compare to the null hypothesis (0 change).

-----------------------------	---

**Date of Protocol:** 12 September 2017

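### WHT versus MPM compares one programme with several clinics, yet neither the models nor the detectable effects allow for clinic; if change over time varies by clinic, the precision is overstated, and the contrast cannot isolate WHT.

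*Combined protocol and SAP*

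**What the plan says.** The design is a "prospective, non-randomized, non-blinded trial with historic and concurrent controls" (Study Design). The group list under Patient Population defines the two arms of the concurrent contrast as follows:

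- "WHT treatment group: patients admitted to the MPP during a predefined 12-month period who consented to participate in the study"
- "MPM control group: patients from MPM clinics within Geisinger during the same 12-month period"

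Study Sites gives "1 site, the Multidisciplinary Pain Program at Geisinger Health System". Sample Size plans "at least 240 WHT patients, 1000 MPM patients, and 150 historic MPP patients" with 10% drop-out. It quotes detectable effects at 80% power from a repeated measures ANOVA with an omnibus F test, for example "NPS: 0.35 versus MPM; 0.42 versus historic MPP". The corresponding MPM figures are 1.40 for the PHQ and 11.51 for MEQs.

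For the analysis, "Repeated measures models will be used to generate point estimates and 95% confidence intervals (CIs) for least square mean (LSM) differences". Adjustment is for patient characteristics that differ at baseline. The utilization and cost paragraph also refers to GLM techniques for matched groups. No matching procedure is described, and clinic is not mentioned there or elsewhere in the methods.

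**The concern.** No MPM patient receives WHT, and every WHT patient is in the MPP, so treatment varies between programmes and never within one. Part of the intervention also works through the clinician, by way of dashboards and alerts. Outcomes such as opioid use, visits and pharmacy orders depend on clinicians' decisions, and control data come from routine records. Patients of the same clinic may therefore change in similar ways over the year.

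A stable difference in level between clinics largely cancels from change from baseline and from the group-by-time interaction. Clinic-by-time variation does not cancel. Where it exists, a model that treats patients as independent overstates the information in the 900 evaluable MPM patients. It also ignores that all WHT patients share one programme.

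Two things are at stake. One is the precision of the MPM contrast on all three primary endpoints and, in principle, on utilization and cost. The other is what the contrast can be said to show, since the objective concerns adding WHT to the MPP.

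**Working it through.** **Inputs from the synopsis.** 240 WHT and 1000 MPM patients with 10% drop-out: 240 × 0.9 = 216 and 1000 × 0.9 = 900 evaluable. Power 80%. MPM detectable effects: NPS 0.35, PHQ 1.40, MEQs 11.51.

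**Assumptions, because the documents do not give them.** Two-sided 5% (suggested by the 95% intervals); k = 5 to 15 MPM clinics of equal size; ICC of the change score 0.001 to 0.05; a 1-df normal approximation in place of the omnibus F test.

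**1. The plan's own figures.** They cannot be reproduced, since no SD, within-patient correlation, alpha or number of time points is stated. They can only be inverted. With independent patients, detectable effect = (1.960 + 0.842) × SD × √(1/216 + 1/900), and the root is √(0.004630 + 0.001111) = 0.0758. The implied SDs are 1.65 (NPS), 6.60 (PHQ) and 54.2 (MEQs). With one SD per endpoint, the ratio of historic to MPM detectable effects would be √(1/216 + 1/135) / 0.0758 = 1.45. The stated ratios are 0.42/0.35 = 1.20, 1.81/1.40 = 1.29 and 17.58/11.51 = 1.53, so some unstated input differs between comparisons.

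**2. Clustering in the MPM arm only.**

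SE ratio = √{ [1/216 + (1 + (900/k − 1) × ICC)/900] / [1/216 + 1/900] }

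Actual size of a nominal 5% test = 2 × [1 − Φ(1.96/ratio)]. The detectable effect is multiplied by the ratio.

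Example, k = 10 and ICC = 0.02: design effect 1 + 89 × 0.02 = 2.78; variance factor 0.004630 + 2.78/900 = 0.007719; ratio √(0.007719/0.005741) = 1.16.

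**3. The MPP counted as one further cluster of 216.** Replace 1/216 in the numerator by (1 + 215 × ICC)/216. This treats the MPP as one draw from the same distribution of clinics. Example, k = 5 and ICC = 0.01: MPP design effect 3.15, MPM design effect 2.79; variance factor 3.15/216 + 2.79/900 = 0.017683; ratio √(0.017683/0.005741) = 1.76.

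| ICC | k | MPM only: SE ratio | Size | NPS | With MPP as a cluster: SE ratio | NPS |
|---|---|---|---|---|---|---|
| 0 | any | 1.00 | 5.0% | 0.35 | 1.00 | 0.35 |
| 0.001 | 15 | 1.01 | 5.1% | 0.35 | 1.09 | 0.38 |
| 0.001 | 5 | 1.02 | 5.4% | 0.36 | 1.10 | 0.38 |
| 0.01 | 15 | 1.06 | 6.3% | 0.37 | 1.69 | 0.59 |
| 0.01 | 5 | 1.16 | 9.1% | 0.41 | 1.76 | 0.61 |
| 0.02 | 10 | 1.16 | 9.1% | 0.41 | 2.19 | 0.77 |
| 0.05 | 15 | 1.25 | 11.8% | 0.44 | 3.20 | 1.12 |
| 0.05 | 5 | 1.65 | 23.6% | 0.58 | 3.38 | 1.18 |

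For ICC 0.01 to 0.05 the other endpoints run as follows. MPM only: PHQ 1.48-2.31, MEQs 12.2-19.0. With the MPP as a cluster: PHQ 2.36-4.73, MEQs 19.4-38.9.

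**4. Few clinics.** If the between-clinic variance is estimated on k − 1 degrees of freedom, the detectable effect grows by a further factor (t at 0.975 + t at 0.80)/2.802. This is about 1.08 for 15 clinics and 1.33 for 5. The table does not include it.

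**The case against.** **The premise is assumed.** No ICC or clinic count is given, and at ICC 0.001 with MPM clustering alone the effect is negligible (size at most 5.4%). This stands. A reader might infer that the intervals are too narrow as a matter of fact. The documents support only the conditional statement, and only clinic-by-time variation counts.

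**The calculation is not the planned test.** It uses a 1-df approximation, while the plan powers an omnibus F test and states no alpha. This also stands: the sizes are illustrative. Nothing was calculated for count or cost models, so for those outcomes only the direction can be argued.

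**The plan does mention another dependence.** The matched-groups wording means one cannot say that the models allow for nothing but repeated measures. It still does not cover clinic.

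**The real problem is confounding.** In a declared non-randomized design, the difference between MPP and MPM care is bias, and wider intervals do not remove it. This is right, and it limits the remedy. A reader might expect a random clinic effect to settle the matter. It cannot, because with a single treated programme the MPP's own effect is inseparable from WHT. Between-clinic variance can be estimated only among MPM clinics. The historic MPP control is the plan's partial answer, since it comes from the same programme.

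**The single site might look like an error.** A reader might set "1 site, the Multidisciplinary Pain Program at Geisinger Health System" against the plural MPM clinics and call it a contradiction. The documents do not show one: control data are taken retrospectively from the EHR, so one conducting site is compatible with controls from several clinics.

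**Conclusion.** The point holds conditionally. The structure is plain from the text: one treated programme, several control clinics, and no allowance for clinic in either the models or the detectable effects. With any positive ICC in change over time, the MPM contrast is less precise than the plan claims.

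The size is not known. Over the assumed ranges it runs from trivial (SE ratio 1.01 at ICC 0.001, MPM clustering only) to severe (about 3.4 at ICC 0.05 with the MPP as a cluster). The MPP's single-cluster status matters more than the number of MPM clinics: at ICC 0.01 it moves the ratio from 1.06-1.16 to 1.69-1.76. At ICC 0 the stated figures are unaffected.

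Whatever the ICC, WHT versus MPM compares MPP plus WHT with MPM care. The clustering point does not carry over to the historic MPP contrast, where the split is by calendar period within one programme.

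**What to change.** - **Analysis.** Record the MPM clinic from the EHR. In the Aim 1 models that use MPM patients, account for clinic-by-time variation among them, with small-sample degrees of freedom.
- **Sample size.** State the number of MPM clinics. Label the three MPM detectable effects as assuming no clinic correlation. Give an ICC sensitivity range for them and for the confidence intervals, including a version with the MPP as a single cluster.
- **Interpretation.** State that WHT versus MPM cannot separate WHT from programme. A claim about adding WHT to the MPP must rest on the historic MPP contrast, which has its own calendar-period limitation.

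The cost is SAP wording, one EHR field and restated figures; no new patients are needed. The downside is that the MPM contrast becomes less precise, possibly much less, and supports a narrower claim.

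### The gamma distribution named for quarterly component costs does not admit zeros, and the plan does not say how zero-cost quarters, which will dominate inpatient cost, are kept in the analysis

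*Combined protocol and SAP*

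**What the plan says.** All references are to the Protocol Synopsis.

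- Objectives: part of the aim is "reductions in healthcare utilization and costs".
- Outcome Measures, in the list of resource-utilisation endpoints, has this entry for cost: "A difference in the change in healthcare costs over time (quarterly) from baseline to M12: total, inpatient, outpatient, rehabilitation, and pharmacy".
- Statistical Methods, on costs: "For cost outcomes, a log-link function with a gamma distribution will be used". No rule for zero costs follows.
- Statistical Methods, on utilisation counts: "a log-link function with a Poisson or negative binomial distribution will be used". Both distributions admit zeros.
- Statistical Methods, for everything else about these endpoints: "Otherwise, the same techniques described above (eg, GLM methods to account for matched groups, estimates, and CIs) will be used". The techniques referred to include "Repeated measures models will be used to generate point estimates and 95% confidence intervals (CIs) for least square mean (LSM) differences". Neither sentence says whether the fit is by full likelihood (for example with random effects) or by GEE or quasi-likelihood.
- The choice of "generalized linear modeling or nonparametric methods (depending on the score distributions) will be used to compare outcomes across the cohorts" is written for primary and secondary outcomes. It sets no rule for zero costs, and a rank-based method would not estimate mean cost.

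**The concern.** One distribution is named for five cost series that behave differently. Total quarterly cost in a chronic pain clinic population will seldom be zero. Inpatient cost will be zero in most patient-quarters, and rehabilitation cost may often be zero too. The documents give no rates for either.

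An analyst who follows the cost sentence and meets zeros can drop them, add a constant, or keep them under a quasi-likelihood fit, and can claim to have followed the plan in each case. These choices do not estimate the same thing. Keeping the zeros compares mean inpatient cost per patient. Dropping them compares mean inpatient cost among patients who were admitted. If the wearable technology saves money by preventing admissions, the saving lies in the quarters that the second analysis discards, and a ratio near 1 would be read as no saving. In a non-randomised, unblinded study whose control data are taken retrospectively from the health record, that choice should be fixed in advance.

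**Working it through.** The documents state no power, zero share or admission rate for cost, so there is no figure of theirs to reproduce.

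**1. Gamma at zero.** The log-density contains (shape − 1) × log(y). At y = 0 it is +infinity for shape 0.5 and −infinity for shape 2; for any shape, P(Y = 0) = 0. The log-link gamma estimating equation, Σ x(y − μ)/μ = 0, is still defined at y = 0. In a simulated set of 2,000 records with 125 positive, a gamma GLM kept all records and returned the ratio of means, 0.643, with an infinite log-likelihood. On the positive records alone it gave 0.965. In another simulated set, adding 100 to every cost moved the ratio from 0.66 to 0.69.

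**2. Share of zero quarters.** If a fraction h of patients is admitted in a year (assumption), the zero share per quarter is (1 − h)^0.25:
- h = 0.15: 0.960
- h = 0.20: 0.946
- h = 0.30: 0.915

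On a Poisson basis the share is exp(−rate/4). It falls below one half only above 4 × ln 2 = 2.77 admissions per patient-year.

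**3. What dropping zeros does to the estimand.** Let p be the probability of any inpatient cost in a quarter and m the mean cost when there is some. The all-patient mean is p × m. The between-group ratio of changes is then [change in p, WHT / change in p, control] × [change in m, WHT / change in m, control]. A users-only fit estimates the second bracket alone.

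Assumed scenarios, with p falling in WHT only and m unchanged:
- 8% to 5%: all-patient ratio 0.05/0.08 = 0.625; users-only ratio 1.
- 6% to 3%: all-patient ratio 0.03/0.06 = 0.50; users-only ratio 1.

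**4. Simulation at the planned sizes.** Sample Size gives "Sample size estimated to be at least 240 WHT patients, 1000 MPM patients, and 150 historic MPP patients" with 10% drop-out: 240 × 0.9 = 216, 1000 × 0.9 = 900, 150 × 0.9 = 135. Further assumptions: one baseline and four follow-up quarters, follow-up pooled, gamma patient frailty with variance 0.8, cost-per-admission coefficient of variation (CV) 1, no covariates, 3,000-4,000 runs.

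| Comparator | True ratio | Median, zeros kept | Median, zeros dropped | Users-only 95% CI contains true all-patient ratio |
|---|---|---|---|---|
| MPM | 0.625 | 0.633 | 1.010 | 62.3% |
| MPM | 0.50 | 0.506 | 1.023 | 47.2% |
| Historic MPP | 0.625 | 0.612 | 0.988 | 76.5% |
| Historic MPP | 0.50 | 0.476-0.484 | 0.975-0.990 | 66.9-67.2% |

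Repeat runs at CV 1 gave about 0.62-0.65 and 0.48-0.51 with zeros kept, and 0.97-1.02 with zeros dropped. At CV 2, the zeros-kept medians against historic MPP were 0.584 (true 0.625) and 0.457 (true 0.50), about 7% and 9% low.

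**5. Precision once zeros are kept.** Expected baseline-quarter admissions are 216 × 0.08 = 17.3 or 216 × 0.06 = 13.0 in WHT, and 135 × 0.08 = 10.8 or 135 × 0.06 = 8.1 in historic MPP. Against historic MPP, the middle 95% of estimates is:
- pooled over follow-up: 0.16-2.05 (true 0.625) and 0.10-2.15 (true 0.50);
- one follow-up quarter against baseline: about 0.10-3.1 and 0.04-3.8.

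Power for the pooled contrast, with jackknife standard errors, is 10-12% against historic MPP and 18-24% against MPM. For a single quarter it is about 7% and 10%.

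**6. Standard errors with zeros kept (pooled).** Coverage of the nominal 95% interval at CV 1 is 92.5-94.3% with the robust standard error and 95.3-96.2% with a delete-one-patient jackknife. At CV 2 it is 84.9-90.7% and 93.4-94.7%.

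**The case against.** The strongest answer is that the plan's own words already permit a sound analysis. It names a log link, a gamma family, GLM methods and repeated measures. A log-link GEE with gamma variance fits that description, keeps every zero and estimates the all-patient ratio. This stands. A reader might infer that the plan drops zeros, or that the gamma specification must be discarded. The documents support neither: nothing says that zeros are removed, and the users-only figures above apply only if they are. What remains is that the named distribution, taken as a likelihood, cannot generate most of the inpatient data, and the plan does not say which fit is meant.

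It can also be said that the consequence is limited. Costs are listed apart from the primary and secondary clinical endpoints. Fewer admissions would show directly in the hospitalisation count, whose models admit zeros; a Poisson approximation that ignores frailty gives that contrast 19-27% power against historic MPP and 32-46% against MPM. This stands too, and it lowers the weight of the point, but the count does not measure cost, which is part of the objective.

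Third, only synopsis-level methods are available here. A fuller methods section that retains zeros would answer the point.

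Finally, a reader might conclude that jackknife standard errors must be required. The simulations were unadjusted, whereas the plan calls for adjustment for baseline differences, and at CV 1 the shortfall of the robust interval is small. They support a check, not a requirement.

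**Conclusion.** The concern holds as a mismatch between the named distribution and the inpatient cost endpoint, with the handling of zeros left open. It does not hold as a claim that the planned analysis will be biased.

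If zeros were dropped, a true all-patient ratio of 0.50-0.625 would be estimated at about 1.0. This rests on the assumed admission rates and on cost per admission being unchanged. That most inpatient quarters are zero is itself an inference, but it needs only an average below about 2.8 admissions per patient-year.

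Keeping the zeros restores the right quantity. It does not make the inpatient contrast precise, and with very skewed costs the median estimate can still be several per cent low. The weight is moderate: worth correcting before data extraction, for a resource-utilisation endpoint only.

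**What to change.** Amend the cost sentence in Statistical Methods to say that:

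1. All zero-cost patient-quarters are retained.
2. All-patient mean cost ratios are estimated by one method, chosen before control data are extracted: either a log-link GEE with gamma-type variance and patient-clustered standard errors, or a two-part model (any cost, then gamma on positive costs) combined into an all-patient mean. Without covariates the two give the same point estimate. That equality was not shown for the planned covariate-adjusted models, so the choice should be made explicitly.
3. The planned covariate adjustment applies.
4. For inpatient cost, a baseline-versus-follow-up contrast pooled over quarters is reported, with a statement that its interval, above all against historic MPP, will be wide.

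A small-sample variance correction, such as a patient-level jackknife, is advisable as a check because admissions are few.

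The cost is wording and slightly more programming; the jackknife needs 216 + 135 = 351 or 216 + 900 = 1,116 refits. A two-part result is harder to report than a single ratio. No extra patients, data or procedures are needed.
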